2.14 Columns in Tables

The following columns will be used for tables, if not stated otherwise:

- Part A: Pooled Placebo column (over all dose levels), Cohort 1 BT200, Cohort 2 BT200, Cohort 3 BT200, Cohort 4 BT200, Cohort 5 BT200, Cohort 6 BT200, Cohort 7 BT200, Cohort 8 BT200, Cohort 9 BT200 and Cohort 10 BT200.
- Part B: Pooled Placebo (over all dose levels), Cohort 13 BT200, Cohort 14 BT200 and Pooled BT200 (all subjects treated with BT200 over all dose levels).
- Part C: Cohort 12 BT200 and Placebo column.
- Part D: Cohort 11 BT200 and Placebo column.

In each analysis part, a column showing all subjects together will additionally be used in the table summarizing the demographic information.

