Cohort 3	Loading Placebo or BT200 Dose ²	Maintenance Placebo or BT200 Dose SC injection or IV ²														
13	12.0 mg IV + 12.0 mg SC	12.0 mg	↓	↓	↓	↓	↓	↓								
14	24.0 mg IV + 24.0 mg SC	24.0 mg			↓	↓	↓	↓	↓							

STUDY PART D	Part D Study Duration (Relative Weeks)	W1	W2	W3	W 4	W5	W 6	W7	W 8	End of Part D
Cohort ⁵	Single Placebo or BT200 Dose IV ²									
	N=8									
11	24.0 mg	↓								
STUDY PART C	Part C Study Duration (Relative Weeks)	W1	W2	W3	W 4	W5	W 6	W7	W 8	End of Part C
Cohort ⁴	Single Dose SC injection ²									
	N=8 per Cohort									
12	Placebo or BT200: 48.0 mg SC injection									
	Desmopressin: 0.3 µg/kg IV									

Abbreviations: ↓=dosing; DSMB=Data and Safety Monitoring Board; IV=intravenous(ly); N/A=not applicable; NHV=normal human volunteer; SC=subcutaneous(ly); W=week

1. Part A Cohorts will also include NHVs treated with placebo (N=2 for all Cohorts). Each cohort will include a sentinel pair, with a randomization ratio of 1:1 for BT200 to placebo. All dose cohorts will receive a single SC dose of BT200 or placebo on Day 0 of Week 1 (Cohort 1), Week 2 (Cohort 2), Week 3 (Cohort 3), Week 4 (Cohort 4), Week 5 (Cohort 5), Week 6 (Cohort 6), Week 7 (Cohort 7), Week 9 (Cohort 8), Week 10 (Cohort 9), Week 11 (Cohort 10).).
2. In this figure, BT200 doses are shown for each cohort.
3. Part B Cohorts will also include NHVs treated with placebo (N=2 for Cohorts 13 and 14). Both dose cohorts will receive total of 6 doses of BT200 or placebo, comprising the split IV + SC loading dose Day 0 and maintenance SC doses as follows: 4 doses every 7 days of Weeks 1 to 5 (Cohort 13) and Weeks 3 to 7 (Cohort 14).
4. Part C Cohorts will also include NHVs treated with placebo (N=2 for Cohort 12 [BT200 + desmopressin challenge] All subjects will receive only a single SC injection of BT200 or placebo on Day -4 of Week 1. All subjects will receive desmopressin by IV infusion over 30 minutes on Day 0 of Week 1 (Cohort 12) at approximately 96 hours after the single dose of BT200 or placebo.
5. Part D Cohort 11 will also include NHVs treated with placebo (N=2). This cohort will receive BT200 or placebo administered as an IV infusion over 24 hours on Day 0 of Week 1.

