1.2 Study Design

Study BT200-01 is a prospective, double-blind, randomized, placebo-controlled First-In-Human (FIH) study of BT200 in male and female NHVs with 4 sub-parts: Part A, a single ascending dose (SAD) study; Part B, a multiple ascending dose (MAD) study; Part C, a desmopressin challenge study; and Part D, a relative Bioavailability (BA) study.

Part A, the SAD study in NHVs, will be conducted according to an ascending dose cohort paradigm in which a unique cohort of NHVs will be treated at each single dose level. There will be 10 cohorts of NHVs (6:2 ratio of BT200:placebo; except for the sentinel pair [1:1 ratio]). Cohorts 1 through 10 will consist of 8 NHVs each, comprising 6 NHVs administered BT200 subcutaneous (SC) (0.18, 0.6, 1.8, 6.0, 12.0, 18.0, 24.0 by rapid SC injection, and 24.0, 36.0 mg, 48.0 mg by gradual SC infusion, respectively, for each cohort) and 2 NHVs administered placebo SC. Not all NHVs in a given cohort in Part A will be dosed on the same day: a sentinel pair (1 BT200, 1 placebo) will be dosed on the first day, then with a lag of at least 48 hours staggered groups roughly of 2 to 3 NHVs per day will be dosed thereafter. Cohorts 8-10 of Part A will be initiated only after submission and authorization of a Substantial Amendment to Ethics Committee (EC) and Austrian Agency for Health and Food Safety (AGES) summarizing the results of Cohorts 1-7.

Part B, the MAD study in NHVs, will also be conducted according to an ascending dose cohort paradigm. Part B will be initiated only after Substantial Amendment to EC and AGES has been submitted and authorized following completion of cohorts 8-10 of Part A and Part D. There will be 2 cohorts of NHVs, each consisting of 8 NHVs (6:2

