1.4 Sample Size Calculation

As this study is exploratory and descriptive in nature, no inferential statistical testing was planned and therefore an exact sample size requirement cannot be specified. The number of NHVs planned to be included is expected to be sufficient to fulfill the study's objectives, but not excessive.

Part A: 80 NHVs; Part B: 16 NHVs; Part C: 8 NHVs; Part D: 8 NHVs (including NHVs who may have previously participated in Part A).

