2.5 Blinding and Randomization

Subjects and study staff will be blinded to treatment assignment. Injections and infusions of BT200 or placebo will have a similar appearance. Unblinding for Part A and D will be performed after data entry for the respective study part is complete and database snapshot was performed for topline analysis. Unblinding for Part B and C will be performed after data entry for the respective study part is complete and database closure was performed.

In Part A, NHVs will be randomized to treatment with BT200 or placebo in a ratio of 3:1 in Cohorts 1 and 2, and in a ratio of 6:2 in Cohorts 3 to 10, except for the sentinel pair of subjects (1:1 ratio). For each of the remaining study parts (Parts B, C, and D), NHVs will be randomized to treatment with BT200 or placebo in a ratio of 6:2. If the site is able to recruit Asians in addition to Caucasians, a stratified randomization procedure will be performed according to Ethnicity. This stratification is not performed formally within the randomization list, but the sites instructed to not consider Asians for the sentinel pairs (to increase probability for Asians to not receive placebo).

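### The single Part A placebo column mixes 14 injected with 6 infused placebo subjects, so infusion Cohorts 8-10 have no procedure-matched, concurrent placebo summary

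*SAP*

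**What the plan says.** SAP 1.2 sets out ten Part A cohorts at 6:2: "There will be 10 cohorts of NHVs (6:2 ratio of BT200:placebo; except for the sentinel pair [1:1 ratio"]). It adds that "Cohorts 1 through 10 will consist of 8 NHVs each". The procedure changes partway through the dose sequence: "24.0 by rapid SC injection, and 24.0, 36.0 mg, 48.0 mg by gradual SC infusion". Cohorts 1-7 are therefore injection cohorts and Cohorts 8-10 infusion cohorts, and Cohorts 7 and 8 share the 24 mg dose and differ in procedure. The same section has Cohorts 8-10 start only after a planned DSMB review of Cohorts 1-7 and an authorised Substantial Amendment. Footnote 1 of the protocol's Study Diagram fixes the placebo numbers: "Part A Cohorts will also include NHVs treated with placebo (N=2 for all Cohorts").

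SAP 2.14 then sets the table layout, introduced by "The following columns will be used for tables, if not stated otherwise". For Part A it specifies "Part A: Pooled Placebo column (over all dose levels"), followed by one BT200 column for each of Cohorts 1 to 10. The table list in SAP 7.1 names no other placebo column for the Part A safety, laboratory, vital-sign or pharmacodynamic tables.

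**The concern.** Pooling placebo across dose levels is ordinary practice in an ascending-dose study, because placebo has no dose. That reasoning does not cover a change in how the injection volume is delivered. A slow subcutaneous infusion and a rapid injection may differ in local reactions, procedure-related adverse events or vital signs, with or without active drug. Cohorts 8-10 also ran later, so the pooled column mixes period as well as procedure.

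Safety and tolerability is the primary endpoint (SAP 1.3.1). The adverse event overview, the maximum-severity tables and the bleeding-event table carry 95% confidence intervals (SAP 7.1), which invites comparison between columns. If the procedure matters, part of any gap between Cohorts 8-10 and placebo would reflect delivery and not BT200. The error could run either way: it could suggest a drug effect, or mask one in the highest-dose cohorts. The design randomised placebo within every cohort, so the matched controls exist; the tables do not summarise them.

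**Working it through.** **Planned numbers.** SAP 1.4 gives "Part A: 80 NHVs; Part B: 16 NHVs; Part C: 8 NHVs; Part D: 8 NHVs". For Part A, 10 cohorts × 8 = 80, which reproduces the stated figure.

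- Placebo in injection cohorts: 7 × 2 = 14
- Placebo in infusion cohorts: 3 × 2 = 6
- Total 20, of which 14/20 = 70% injected and 6/20 = 30% infused

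SAP 2.5 words the ratio as 3:1 for Cohorts 1 and 2 and 6:2 for the rest. These are the same proportion, so two of eight are on placebo either way.

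**Was placebo infused in Cohorts 8-10?** No sentence says so outright. The study is double-blind, the Study Diagram heads the Part A dose column as placebo or BT200, and SAP 2.5 states "Injections and infusions of BT200 or placebo will have a similar appearance". I infer that placebo followed the procedure of its cohort.

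**Apparent difference with an inert drug.** Let *p_inj* and *p_inf* be the event rates due to each procedure alone.

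- Pooled placebo rate = 0.7 *p_inj* + 0.3 *p_inf*
- Cohorts 8-10 minus pooled = *p_inf* − (0.7 *p_inj* + 0.3 *p_inf*) = 0.7 (*p_inf* − *p_inj*)
- Cohorts 1-7 minus pooled = *p_inj* − (0.7 *p_inj* + 0.3 *p_inf*) = −0.3 (*p_inf* − *p_inj*)

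The documents give no rates, so all of these are assumed:

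| Injection / infusion rate | Pooled placebo | Cohorts 8-10 | Cohorts 1-7 |
|---|---|---|---|
| 10% / 10% | 10% | 0 | 0 |
| 10% / 20% | 13% | +7 points | −3 points |
| 10% / 40% | 19% | +21 points | −9 points |
| 30% / 10% | 24% | −14 points | +6 points |

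**What splitting costs in precision.** SAP 2.7 names Altman for the intervals without giving a formula, so two standard types are shown. Upper 95% limits with zero events:

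| Placebo group | Wilson | Clopper-Pearson |
|---|---|---|
| 0/20 | 16.1% | 16.8% |
| 0/14 | 21.5% | 23.2% |
| 0/6 | 39.0% | 45.9% |

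**Which reference is closer to the true infusion-placebo rate?** Root mean squared error:

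- Pooled (n=20): √{[0.7 (*p_inf* − *p_inj*)]² + [14 *p_inj*(1 − *p_inj*) + 6 *p_inf*(1 − *p_inf*)]/400}
- Infusion only (n=6): √{*p_inf*(1 − *p_inf*)/6}

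| Injection / infusion rate | Pooled | Infusion only |
|---|---|---|
| 10% / 20% | 10.2 points | 16.3 points |
| 10% / 30% | 16.1 points | 18.7 points |
| 10% / 40% | 22.6 points | 20.0 points |

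With 10% after injection, the two break even near 35% after infusion.

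For a continuous measure such as a vital sign, the standard error of one six-subject BT200 cohort minus placebo is √(1/6 + 1/20) = 0.465 SD with pooled placebo and √(1/6 + 1/6) = 0.577 SD with infusion placebo. Setting 0.49 *d*² = 1/6 − 1/20 gives *d* ≈ 0.49 SD, the procedure effect above which the matched column has the smaller mean squared error.

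**The case against.** The strongest reply is that no planned estimate is biased. SAP 1.4 calls the study descriptive with no inferential testing, and the SAP defines no BT200-minus-placebo contrast. Any excess is one a reader forms by eye. This stands and limits the weight of the point, but these columns and their intervals are the whole planned safety summary for the primary endpoint.

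Second, the procedure effect is unknown and may be nil. For modest effects the pooled column is the more accurate reference, as the error comparison shows. This also stands. It rules out replacing the pooled column, or naming the six infused subjects as the sole reference, but not showing the matched columns beside it.

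Third, the listings are sorted by cohort and carry treatment group (SAP 2.13), so the 14 and the 6 can be separated by hand, and the two 24 mg columns can be compared directly. Both are true. However, a listing is not a summary, and the 24 mg comparison is on active drug only.

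Fourth, the case is weaker for some tables. Local reactions are the clearest example, and the SAP lists no separate local-tolerability table. There is little reason to expect delivery speed to alter bleeding. Bleeding is included because SAP 6.2 analyses it together with adverse events.

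A reader might also infer that every Part A table is affected. SAP 2.14 sets a default only, and the screening-failure table, for one, uses a single column for all subjects. Nor do the documents describe the trial being halted before Cohort 8; they describe a scheduled review and an amendment.

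**Conclusion.** The point holds as a gap in the default Part A table layout. BT200 is shown by procedure, placebo is not, and 70% of the placebo column comes from the other procedure when Cohorts 8-10 are read. The distortion is 0.7 times the procedure effect in Cohorts 8-10 and 0.3 times with opposite sign in Cohorts 1-7. Over the assumed rates it runs from zero to 21 points in size.

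This rests on planned counts, on the inference that placebo was infused in Cohorts 8-10, and on rates that the documents do not supply. It would be tempting to conclude that the safety results are biased or that the pooled column is wrong. The documents support neither: there is no formal comparison to bias, and no evidence that the procedures differ in placebo subjects. The change is worth making because it is cheap and bears on the primary endpoint.

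**What to change.** Keep the pooled placebo column. Add two columns, *Placebo SC injection (Cohorts 1-7, n=14)* and *Placebo SC infusion (Cohorts 8-10, n=6)*, to the Part A adverse event and bleeding tables (14.1.3.1.1 to 14.1.3.1.18) and the vital-sign tables (14.1.3.1.32 to 14.1.3.1.34). Add one sentence to SAP 2.14 saying that each BT200 cohort is read against both the pooled and the procedure-matched placebo, and that the matched column supplements the pooled one.

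The cost is two columns and one sentence, with no new subjects, visits or data. The downside is that six subjects give very wide intervals. The sentence should say so, to keep readers from over-interpreting a zero or a single event in the infusion-placebo column.

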2.15 Changes in the Conduct of the Study or Planned Analysis

No changes to the statistical analysis as compared to CSP are planned.

2.16 Effect of Covid-19

Due to the Covid-19 pandemic no monitoring visits can be performed before database snapshot for topline analyses. Possible impact of Covid-19 pandemic and respective measures were discussed. Subject visits and time points will be partly affected by the pandemic. If visits can not be performed due to Covid-19 the visit will be documented as not performed in the eCFR with reason "COVID19". Drop-outs due to Covid-19 will be documented in the eCRF on the end of study page with reason "other" and specification "COVID19" as reason for early termination. No further effects are expected due to Covid-19. Statistical analysis will include a summary of drop-outs and early terminations due to Covid-19. In Part B and C, a screening for coronavirus by nasal swab testing will be performed at the screening visit. Subjects with positive coronavirus test will be excluded from the study. The results of the coronavirus screening will be tabulated and listed.

Unexpected Covid-19 effects (e.g. overviews on missing data, Covid-19 related protocol deviations, missed visits, visits out of time-window and changes in study processes) will be described in the Clinical Study Report.

3. OVERALL STUDY INFORMATION

Tables will be provided for the Safety Population, if not stated otherwise and selected tables will be repeated for the PP Population. The following information will be analyzed descriptively and corresponding details on the subject level will be provided in data listings:

- Patient overview
- Screening failures
- Violated inclusion/exclusion criteria (will only be listed)
- Subjects by dose level and overall
- Study visit information (incl. Admission/Discharge Inpatient Unit information)
- Missed visits due to Covid-19 (will be listed only)
- End of study information (incl. drop-outs due to Covid-19)
- Protocol deviations
- Coronavirus screening (only applicable for Part B and C)

Specifications of Tables, Listings and Figures (TLFs) are provided in Section [7](#).

4. BASELINE EVALUATION

Baseline data will be presented for Safety Population .

4.1 Data Points

Data will be analyzed from the screening visit and the randomization visit (if applicable) The following information will be analyzed descriptively and corresponding details on the subject level will be provided in data listings:

- Demographics (including body height [cm] and body weight [kg], Body Mass Index (BMI) [kg/m²])
- Serology (will only be listed)
- Medical history overall and by SOC and PT
- Prior/Concomitant medications overall and by ATC level
- Prior/Concomitant procedures overall and by SOC and PT
- Childbearing-potential (will only be listed)

Vital signs, ECG and physical examination results will be analyzed in the safety section (see Section [6.4](#)).

Specifications of TLFs are provided in Section [7](#).

4.2 Derivations and Definitions

- Medications stopped clearly prior to first study drug administration will be considered as prior medications, all other medications are considered to be concomitant. Medications with a missing or incomplete stop date where it cannot clearly be decided if the stop date was before or after Day 0 (Visit 1) will be considered as concomitant.
- Procedures stopped clearly prior to first study drug administration will be considered as prior procedures, all other procedures are considered to be concomitant. Procedures with a missing or incomplete stop date where it cannot clearly be decided if the stop date was before or after Day 0 (Visit 1) will be considered as concomitant.
- BMI [kg/m²] is defined as the weight [kg] divided by the square of the body height [m]

5. PHARMACOKINETICS / PHARMACODYNAMICS / BIOMARKER / IMMUNOGENICITY

Pharmacodynamics, biomarker and immunogenicity analysis will be performed for the PP Population and the Safety Population.

5.1 Pharmacokinetics

Pharmacokinetics analysis will be performed by CERTARA and are not described in this Statistical Analysis Plan.

5.2 Pharmacodynamics

The following tables will be performed for PFA-100, VWF:RiCo [%], multiplate aggregometer and REAADS and corresponding details on the subject level will be provided in data listings:

- Absolute values by time point
- Absolute change from randomization by time point
- Relative change [%] from randomization by time point

The following figures will be provided for PFA-100, VWF:RiCo [%], multiplate aggregometer and REAADS separately:

- Absolute values by subject: For every subject separately, the time course over of the parameters mentioned above will be drawn, where the actual measurement time point since first dose will be shown on x-axis (hours) and the parameters values will be drawn on the y-axis.
- Absolute values by cohort: One graph will be drawn that includes the data of all cohorts. One line will be drawn per cohort, where the x-axis will show the planned time point of measurement (in hours) and the y-axis will show the mean value of the respective cohort incl. standard error. Measurements of all scheduled visits will be included, where the EOS visit will be treated as the last visit.

PD sampling results will be entered eCRF using a result specifier (i.e. <, ≤, >, ≥). For statistical analysis, values reported as <x, ≤x, >x or ≥x will be analyzed as x. E.g. <300, ≤300, >300 or ≥300 will be analyzed as value 300.

Details are specified in Section [7](#).

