ratio of BT200:placebo) in this part of the study. These cohorts will be administered an initial loading dose regimen of BT200 or placebo consisting of both a 2-hour IV infusion and an SC injection on Day 0, followed by 4 weekly (every 7 days) doses of BT200 or placebo by SC injection. The dose levels in Part B are: a loading dose of 12.0 mg IV infused over 2 hours plus 12.0 mg SC injection followed by 4 maintenance doses of 12.0 mg SC injection in Cohort 13; a loading dose of 24.0 mg IV infused over 2 hours plus 24.0 mg SC injection followed by 4 maintenance doses of 24.0 mg SC injection in Cohort 14. Not all subjects in each of the cohorts of Part B will be dosed on the same day; rather, they will be dosed in staggered groups roughly of 2 to 3 subjects per day.

Part C, the desmopressin challenge will be initiated only after a Substantial Amendment to EC and AGES has been submitted and authorized following cohorts 8-10 of Part A and Part D. Part C will consist of a single cohort, Cohort 12, of 8 NHVs (6:2 ratio of BT200:placebo, plus desmopressin challenge) in this part of the study. Six subjects in Cohort 12 will be administered a single dose of 48.0 mg BT200 SC injection and 2 subjects administered a single dose of placebo on Day -4 as an SC injection. All subjects will then be administered an intravenous (IV) infusion of 0.3 μ g/kg desmopressin over 30 minutes on Day 0 approximately 96 hours after the single dose of BT200 or placebo SC (i.e., at the predicted time to maximum plasma concentration [T_{max}] for BT200).

Part D, the relative BA crossover, will be initiated only after a Substantial Amendment to EC and AGES has been submitted and authorized following cohorts 1-7 of Part A. Part D will consist of 1 cohort of NHVs, consisting of 8 NHVs (6:2 ratio of BT200:placebo) administered a single IV dose of BT200 of 24.0 and 2 NHVs administered a single dose of placebo IV over 24 hours on Day 0. Part D could include NHVs who have previously participated in Part A.

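### Do the by-cohort PD and biomarker figures average BT200 and placebo subjects into one line?

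*SAP*

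**What the plan says.** SAP 5.2 defines the by-cohort figure for the four pharmacodynamic assays: "One graph will be drawn that includes the data of all cohorts. One line will be drawn per cohort". It adds that "the y-axis will show the mean value of the respective cohort incl. standard error". SAP 5.3 uses the same words for the seven biomarkers. Both sections refer to Section 7 for details, but the comment cells for these figures in 7.3 are empty.

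In the design sections a cohort includes its placebo subjects:

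- Part A, SAP 1.2: "Cohorts 1 through 10 will consist of 8 NHVs each, comprising 6 NHVs administered BT200 subcutaneous (SC"), the other two receiving placebo. The protocol's Study Diagram, footnote 1, agrees: "Part A Cohorts will also include NHVs treated with placebo (N=2 for all Cohorts").
- Part B, SAP 1.2: two cohorts of eight, also 6:2.
- Part C, SAP 1.2: "Part C will consist of a single cohort, Cohort 12, of 8 NHVs (6:2 ratio of BT200:placebo, plus desmopressin challenge").
- Part D, SAP 1.2: "Part D will consist of 1 cohort of NHVs, consisting of 8 NHVs (6:2 ratio of BT200:placebo").

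SAP 2.5 places the allocation inside the cohort; for Parts B to D, "NHVs will be randomized to treatment with BT200 or placebo in a ratio of 6:2".

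SAP 2.14 does separate the arms: pooled placebo beside each cohort's BT200 subjects in Parts A and B, and one BT200 and one placebo column in Parts C and D. Its opening line limits it to tables: "The following columns will be used for tables, if not stated otherwise".

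**The concern.** Read with the design section's meaning of cohort, the figure rule asks for one mean over all eight subjects. Each line would be pulled toward placebo, its standard error would absorb part of the treatment effect, and no placebo line would exist. Parts C and D, with one cohort each, would show a single mixed line. That would matter most in Part C, where every subject receives desmopressin and only the two placebo subjects show the response without BT200.

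The 7.3 list seems to support this reading, since the safety figures are titled by group and these by cohort. All the by-cohort figures are marked for the topline analysis, which SAP 2.2 plans for Parts A and D. A literal figure would then sit beside a table of the same assay that separates the arms and shows different means.

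**Working it through.** **Counts.** Cohorts × 8 should reproduce the planned sizes in SAP 1.4.

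| Part | Cohorts | Cohorts × 8 | Stated N | BT200 | Placebo |
|---|---|---|---|---|---|
| A | 10 | 80 | 80 | 60 | 20 |
| B | 2 | 16 | 16 | 12 | 4 |
| C | 1 | 8 | 8 | 6 | 2 |
| D | 1 | 8 | 8 | 6 | 2 |

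They agree, so in Section 1.2 placebo subjects are counted in the cohorts. Section 2.5 words the Part A ratio as 3:1 for Cohorts 1 and 2 and 6:2 for the rest; these are the same ratio.

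**What a literal line would show.** The weights are 6/8 = 0.75 for BT200 and 2/8 = 0.25 for placebo, so the line carries 75% of any BT200–placebo difference D. With a common within-arm standard deviation s, the expected variance among the eight subjects is s² + (6 × 2/8) × D²/7, and SE = √(variance/8). The documents give no pharmacodynamic values, so D is an assumption, shown over a range:

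- D = 1s: √((1 + 1.5/7)/8) = 0.39s
- D = 2s: √((1 + 6/7)/8) = 0.48s
- D = 3s: √((1 + 13.5/7)/8) = 0.61s
- BT200 subjects only: 1/√6 = 0.41s

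**Lines per figure, Parts A/B/C/D.** Literal reading: 10/2/1/1, none of them placebo. With the 2.14 groups (leaving out Part B's extra pooled BT200 column): 11/3/2/2, with placebo resting on 20/4/2/2 subjects at full enrolment.

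**Reach.** Section 7.3 lists 4 pharmacodynamic + 7 biomarker = 11 by-cohort figures, numbered once per study part. Eleven is an upper limit: the protocol's summary of changes adds VWF propeptide for Part A, and the schedule footnotes mention an exploratory coagulation assay for Parts A and B but not for C and D.

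**Which reading the outputs support.**

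- Section 2.14 joins cohort numbers only to BT200. Placebo has its own column and is never labelled as belonging to a numbered cohort.
- Listing 16.2.x.1.1 carries an actual and a randomized dose cohort. Subjects are randomized to BT200 or placebo within a cohort, not to a cohort, so this pair makes most sense if dose cohort is a treatment grouping with placebo as one level.
- Table 14.x.1.1.1 has a column for each BT200 dose level and one for placebo.
- Section 2.13 requires a treatment-group column in every listing, yet no listing in 7.2 names one. Nearly all lead with dose cohort or dose level, which most naturally fills that role. Section 2.13 is therefore not evidence for the mixed reading.
- The contrast in 7.3 is mainly one of layout. The safety figures are separate plots for each group, while these overlay all lines on one graph. The SAP also switches between dose cohort and dose level across its listings, so the choice of label proves little.

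Under the usage in these outputs, one line per cohort gives BT200 lines plus a placebo line.

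**The case for a change.** The strongest case for acting is that the grouping is not written anywhere. Cohort has a clear meaning in Section 1.2, and under it the figure rule mixes the arms. Section 2.14 needs the drug name added to its cohort labels to mean BT200 subjects only, and 5.2 and 5.3 leave that out. The referral to Section 7 leads to blank cells, and Section 8 provides no shells. Review of drafts is a safeguard and not a rule, and one sentence would settle the matter.

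The textual part stands: no passage extends 2.14 to these figures, and a clarifying sentence would do no harm. What does not follow is that the figures would come out wrong. The literal reading yields a comparator-free graph in two of the four parts of a placebo-controlled study whose tables of the same assays separate the arms, so a programmer would be unlikely to take it as the instruction. Section 8 also has draft outputs produced on a dummy group allocation and reviewed by the sponsor, and a missing placebo line would be visible on every one of these figures.

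**Conclusion.** No change is needed. The figure sections omit a detail that the rest of the SAP's output specification supplies in practice: BT200 subjects by cohort, with placebo as a separate line. The 75% weight and the altered standard errors are correct arithmetic for a reading that is unlikely to be used.

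Even if a mixed figure were drawn, the damage would be confined to exploratory displays. SAP 1.4 plans no inferential testing. Each of the 11 by-cohort figures has a matching table of absolute values by time point, also marked for topline, in the 2.14 columns; under Section 2.6 it gives n, mean and standard deviation, from which the arm-specific mean and standard error follow. The by-subject figures and the listings are untouched.

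This conclusion rests on two assumptions: that dose cohort in the output sections denotes a treatment grouping, as listing 16.2.x.1.1 and Section 2.14 suggest, and that the draft review in Section 8 takes place as described.
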